### 10.1.1 Primary Estimand

Clinical question of interest: Is there a treatment benefit of CSL312 after IV infusion in patients with COVID-19, i.e. does treatment with CSL312 + SOC reduce the risk to progress to tracheal intubation or to die prior to tracheal intubation in subjects with severe COVID-19 disease while subjects are treated with SOC?

The primary estimand in line with the primary interest of the study follows the treatment policy strategy and is described as follows:

- A. Subject population: the target subject population defined by eligibility criteria.
- B. Treatment condition of interest: One dose (700 mg) of IP (CSL312 + SOC or Placebo + SOC) via IV infusion on peripheral vein.
- C. Variable: subject’s progression to tracheal intubation or death prior to tracheal intubation at any time from randomization to Day 28.
- D. Intercurrent events:
  - 1. Concomitant use of anti-COVID-19 drugs.
  - 2. Early discontinuation of the study for any reason.
  - 3. Randomized without treatment.
- E. Population level summary: risk difference of progression to tracheal intubation or death prior to tracheal intubation (CSL312 + SOC minus placebo + SOC).

In this study, the treatment policy strategy will be used for all intercurrent events. It is reasonable to assume for subjects who are losses to follow-up after hospital discharge likely not to have experienced the event under randomized treatment. If subjects are still in hospital after withdrawal from the study (but not withdrawal of consent), missing data is unlikely to occur.

### 10.1.2 Primary Efficacy Analysis

The primary endpoint for this study is the risk of tracheal intubation or death prior to tracheal intubation from randomization to Day 28. The ITT Analysis Set will be used for the primary efficacy analysis.

Subjects with less than 28 days of the Treatment Period (i.e., who discontinued from the study prematurely) and without documented intubation or death will be considered to not have progressed to tracheal intubation or died prior to tracheal intubation (see Section 10.1.3).

Firth logistic regression model including age as continuous covariate, treatment group, gender (male or female), country (USA or Brazil), and baseline comorbidities (yes or no) as categorical covariates in the model will be used to compare the risks of progression between the 2 treatment groups. Comorbidities will include hypertension, diabetes, and obesity (defined as BMI  $\geq 30$  kg/m^2). A 1-sided p-value will be estimated from the model and the null hypothesis (see Section 4.1.2) will be rejected if that p-value is  $< 0.025$ . The risk difference and associated 2-sided 95% confidence interval (CI) will be estimated using the method described by [Ge et al \[2011\]](#).

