		
 4. Revised inclusion criteria to indicate that the SARS-CoV-2 infection must be determined using a molecular diagnostic test (reverse transcription polymerase chain reaction [RT-PCR] or equivalent) approved by regulatory authorities. 5. Revised inclusion criteria to indicate that the SARS-CoV-2 test may be repeated within the Screening Period if a false negative result is suspected. 6. Revised text regarding early hospital discharge to indicate the data to be obtained via weekly telephone call and by whom. 7. Defined the minimum laboratory results that are required to initiate randomization. 8. Revised study product administration to indicate that the intravenous infusion should be a slow injection, (ie, push of about 3 minutes). 9. Added assessment of outcome measures before dosing on Day 1, including the subject’s use of supplemental oxygen; use of CPAP or BiPAP; use of HFNC; use of ECMO; intubation; and intensive care unit admission. 10. Revised Schedule of Assessments to indicate that pre-existing laboratory results may be used in lieu of repeating the assessments for Screening provided that the assessments were performed with 48 hours of randomization and the subject agrees to the use of those data in the inform consent form. 11. Added stratification by country variable (USA or Brazil) to the planned statistical analyses.
16 September 2020	Amendment 3	
 1. Revised the required duration of the use of acceptable forms of contraception to ≥ 90 days after the last administration of study drug. 2. Added the use a non-contact infrared thermometer to the methods of measuring body temperature.

Clinical Study Protocol Synopsis

Title	A Phase 2, Multicenter, Double-blind, Randomized, Placebo-controlled Study to Evaluate CSL312 in Coronavirus Disease 2019 (COVID-19)
Study Number	CSL312_COVID-19
Sponsor	CSL Behring LLC [name] [name] United States of America
Development Phase	Phase 2
Study Product	CSL312 (Garadacimab, Factor XIIa Antagonist Monoclonal Antibody)
Indication	For the prevention of respiratory failure in patients with COVID-19

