5.1.2 Randomization Procedures

Randomization will be conducted using an IRT. The investigator will be supplied with a user guide for the IRT. Subjects will be randomly assigned to treatment with either CSL312 + SOC or placebo + SOC using a 1:1 randomization ratio and stratified by country (USA or Brazil).

A centralized randomization schedule will be used. The randomization list will be generated according to the approved randomization specifications. The IRT service provider will keep the randomization code on file.

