11.1 Sample Size

There are limited data on the rates of subjects with COVID-19 who progress to tracheal intubation or death prior to tracheal intubation within 28 days. For sample size calculation, a rate of 30% in the control group and a rate of 10% in the CSL312 group have been assumed. With a 2-sided $\alpha = 0.05$ and 1:1 randomization ratio for CSL312 + SOC versus placebo + SOC, a total of 124 subjects need to be randomized (62 subjects to CSL312 + SOC and 62 subjects to placebo + SOC) in order to achieve 80% power to detect a treatment difference using a 2 group chi-square test. For the sample size calculation, it is further confirmed using simulations performed in East[®] 6.5 software (Cytel, Inc.: Waltham, MA) that 80% power is maintained, accounting for the interim analysis for futility and sample size re-estimation.

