11.3 Analyses of Primary Efficacy

The primary endpoint for this study is the incidence of tracheal intubation or death prior to tracheal intubation from randomization to Day 28. The proportion will be calculated as the number of subjects with tracheal intubation or death divided by the total number of subjects for each treatment group. Treatment effect of interest (ie, estimand) is defined as the proportion difference of tracheal intubation or death prior to tracheal intubation (CSL312 + SOC minus placebo + SOC) in the target population regardless of whether additional treatment is used or initial SOC has changed. The ITT Analysis Set will be used for the primary efficacy analyses.

Firth logistic regression model including treatment group; age group as a continuous covariate; gender (male or female); country (USA or Brazil); and Baseline comorbidities (yes or no) as categorical covariates will be used to compare the rates between the 2 treatment groups. Comorbidities include hypertension, diabetes, and obesity (defined as body mass index ≥ 30 [kg/m²]). A 2-sided p-value will be estimated from the model. The proportion difference and associated 95% confidence interval (CI) will be estimated using the method described by Ge et al [2011]. The mITT Analysis Set will be used for primary efficacy endpoint sensitivity analysis.

Sensitivity analyses to assess the effect of missing data will be conducted, for example, by performing tipping point analyses that vary assumptions about the missing outcomes in both study treatment groups.

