### 3 Purpose

This statistical analysis plan (SAP) provides a detailed and complete description of the planned final analysis for the study CSL312\_COVID-19. Mock table, figure, and listing (TFL) shells will be provided in a separate supporting document along with details for the practical implementation of the analyses.

This SAP complies with the International Council for Harmonisation E9 ‘Statistical Principles for Clinical Trials’ and E9 (R1) ‘Statistical Principles for Clinical Trials: Addendum: Estimands and Sensitivity Analysis in Clinical Trials’. It is based upon the following study documents:

- Study Protocol Amendment 2 (dated 25 Aug 2020)
- Case Report Form (CRF), Version 1.0 (dated 03 Jun 2020)
- Independent Data Monitoring Committee (IDMC) SAP 1.0 (dated 28 Aug 2020)
- CSL Behring’s response to comments from the Federal Drug Agency (1.11.3 Clinical Information Amendment)

All decisions regarding the analysis of the study results, as defined in this version of the SAP, have been made before first unblinding for the IDMC analyses.

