## 4.4 Determination of the Initial Sample Size

There are limited data on the rates of subjects with COVID-19 who progress to tracheal intubation or death prior to tracheal intubation within 28 days. For sample size calculation, a rate of 30% in the control group and a rate of 10% in the CSL312 group have been assumed. With a 1-sided  $\alpha = 0.025$  (which is equivalent to a 2-sided  $\alpha = 0.05$ ) and 1:1 randomization ratio for CSL312 + SOC versus placebo + SOC, a total of 124 subjects need to be randomized (62 subjects to CSL312 + SOC and 62 subjects to placebo + SOC) to achieve 80% power to show superiority using a 2 group chi-square test. For the sample size calculation, it is further confirmed using simulations performed in East 6.5 that 80% power is maintained, accounting for the interim analysis for futility and sample size re-estimation.

Depending on the results after the interim analysis, the sample size may be increased up to 248 subjects (124 subjects in CSL312 + SOC and 124 subjects in placebo + SOC).

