### **8.2.3 Baseline Definition**

For efficacy endpoints, baseline is defined as the most recent, non-missing value before randomization (including unscheduled visits) unless otherwise stated. If no value before randomization exists, the most recent, non-missing value before IP administration will be used as baseline value.

For safety, baseline is defined as the most recent, non-missing value before IP administration (including unscheduled visits) unless otherwise stated.

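### The primary model does not adjust for baseline respiratory severity; one prespecified NIAID term would protect the only confirmatory test against chance imbalance at little cost

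*SAP*

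**What the plan says.** SAP 10.1.2 sets the primary analysis as a "Firth logistic regression model including age as continuous covariate, treatment group, gender (male or female), country (USA or Brazil), and baseline comorbidities". Protocol 11.3 gives the same set: "Firth logistic regression model including treatment group; age group as a continuous covariate; gender (male or female); country (USA or Brazil") and comorbidities. The comorbidity flag is a single yes/no for hypertension, diabetes or obesity.

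Protocol 5.1.2 randomizes "using a 1:1 randomization ratio and stratified by country (USA or Brazil"), with no other factor. The sensitivity analyses in SAP 10.1.3 change the analysis set or the handling of missing outcomes and added COVID-19 drugs; none adds a covariate. The subgroups in SAP 8.2.7 are sex, age group, comorbidity, anti-COVID-19 drug use and country.

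The severity data are already planned. SAP 10.2 takes the NIAID score from the CRF, and the summary of improvement by at least 2 points needs a baseline value. SAP 8.2.3 defines that value: "For efficacy endpoints, baseline is defined as the most recent, non-missing value before randomization", with the last value before dosing as fallback. Protocol Amendment 2 "Added assessment of outcome measures before dosing on Day 1", and these measures include supplemental oxygen, CPAP/BiPAP and HFNC use.

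SAP 3 states that its analysis decisions "have been made before first unblinding for the IDMC analyses".

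**The concern.** Subjects can enter on any one of five criteria (Protocol 6.2), so non-intubated subjects may be at NIAID 3 (non-invasive ventilation or high-flow oxygen), 4 or 5. NIAID 3 is the step next to invasive ventilation, so it is a natural candidate for a strong predictor of intubation.

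If the arms differ by chance in the share at NIAID 3, the planned p-value partly reflects that difference. The by-visit NIAID and respiratory tables would show the imbalance, but no visible planned result shows its effect on the primary comparison. An adjustment chosen after unblinding would be post hoc. SAP 10.3 has one confirmatory test, so the study conclusion rests on it.

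**Working it through.** **1. The plan's own figure.** The inputs from Protocol 11.1 and SAP 4.4 are 30% versus 10%, two-sided 0.05 (one-sided 0.025), 1:1 allocation, and "80% power to detect a treatment difference using a 2 group chi-square test". With pooled variance and no continuity correction:

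n per arm = [1.960·√(2·0.20·0.80) + 0.842·√(0.30·0.70 + 0.10·0.90)]² / 0.20² = 61.6, so 62 per arm and 124 in total.

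Power at 62 per arm is 80.3%. The plan's figure reproduces. Expected events are 62·0.30 + 62·0.10 = 24.8.

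**2. How often the arms differ.** The NIAID 3 share is an assumption; the documents do not give it. The chance of a gap of at least 10 percentage points in either direction, from two independent binomials, is:

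| Total N | 5% share | 10% | 20% | 30% | 50% |
|---|---|---|---|---|---|
| 124 | 0.8% | 5.1% | 14.4% | 20.2% | 24.3% |
| 200 | 0.2% | 2.5% | 9.3% | 14.2% | 17.9% |
| 248 | 0.04% | 0.8% | 4.7% | 8.3% | 11.2% |

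Each direction is half of this. The larger sizes are shown because Protocol 11.8 allows an increase up to 200, while under SAP 4.4 "the sample size may be increased up to 248 subjects".

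**3. What a gap does to the test.** This was simulated with Firth logistic regression and a one-sided 0.025 Wald test, 62 per arm, using the planned covariates without and with one binary severity term. Further assumptions:
- Odds ratios are 1.4 per SD of age, 1.3 for sex, 1.2 for country and 1.5 for comorbidity.
- Severity is independent of these covariates.
- Event rates are 30%/10% for power and 20%/20% under the null.
- No interim analysis is modelled.

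At a 30% share, without / with the term:

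| Severity OR | Power, CSL312 at least 10 points sicker | Null rejection, CSL312 at least 10 points healthier |
|---|---|---|
| 1.5 | 74.9 / 77.6% | 2.8 / 2.0% |
| 2 | 72.7 / 78.7% | 3.3 / 2.0% |
| 3 | 68.5 / 79.1% | 4.5 / 2.0% |
| 5 | 62.1 / 80.8% | 5.8 / 1.9% |

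Simulation standard errors are about 0.4 points (power) and 0.1 to 0.2 points (null). Shares of 10% and 50% give similar conditional figures. At N=248 and a 30% share a gap is rarer but matters more when it occurs: null rejection is 3.3 / 2.4% at OR 1.5 and 8.3 / 2.3% at OR 5.

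**4. Averaged over all trials.** The change in power from adding the term, in percentage points:

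| Severity OR | 10% share | 30% | 50% |
|---|---|---|---|
| 1 | −0.3 | −0.3 | −0.5 |
| 1.5 | −0.5 | −0.4 | −0.2 |
| 2 | −0.2 | +0.3 | +0.1 |
| 3 | 0.0 | +1.1 | +1.4 |
| 5 | +1.5 | +2.7 | +2.9 |

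Overall null rejection at a 30% share is 1.9–2.3% without the term and 2.0–2.2% with it.

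**5. A second set of assumptions.** Shares of 20, 35 and 50% with ORs of 2, 4 and 8 give the same pattern. At OR 4, power with CSL312 sicker is about 67% without the term and 79–82% with it. The term also works against the sponsor when chance favours CSL312: at a 35% share and OR 2, power with CSL312 healthier falls from 85.4% to 78.4%.

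**The case against.** **The plan is not wrong.** Sample size and overall type I error stand, and the average power gain is nil or slightly negative up to OR 2. The striking figures condition on a chance event in one direction, and any omitted prognostic variable behaves this way. This is correct, and it is why the point is an improvement.

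**The size is assumed.** Neither the NIAID 3 share nor its odds ratio is in the documents. Exclusion criteria 4 and 6 in Protocol 6.3 remove subjects expected to be intubated or to die very early, which limits the contrast. At a 5% share a 10-point gap occurs in only 0.8% of trials. This also stands, so the figures are ranges.

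**A sensitivity analysis would be enough.** It would supply the missing adjusted result and leave the confirmatory model alone. However, it would not protect the confirmatory test, which would still move with the imbalance.

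**Few events, and the interim.** At 62 subjects about 12 events are expected, the same size as the subgroups for which the term may be dropped. The simulated cost in a 62-subject fit is 0.9 points at OR 1 and 0.1 at OR 3, which is small, but the futility and re-estimation rules were not simulated.

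**Unseen material.** SAP 10.2.3 and 13 are redacted, and the IDMC SAP and the sponsor's response to regulator comments are not available. A severity-adjusted analysis or an earlier discussion of the model could be there. This caveat stands, but the primary, sensitivity and subgroup sections can be read in full and do not cover severity.

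**Conclusion.** The concern holds as a recommended improvement. The primary model has no term for baseline respiratory severity, and neither the randomization nor any visible sensitivity or subgroup analysis fills the gap. The planned test is valid on average, and the case does not rest on average power.

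The benefit is a test that stays near its nominal behaviour when the arms differ by chance. At NIAID 3 shares of 20–50%, that means a 10-point gap in about one trial in seven to one in four at N=124. At OR 1.5 the effect is small. At OR 2 to 3 and a 30% share, the term restores about 6 to 11 points of power when CSL312 is sicker. It also brings null rejection of 3.3–4.5% back to 2.0% when CSL312 is healthier. All of this depends on the assumed share and odds ratio.

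**What to change.** Before first unblinding, add one binary term, baseline NIAID 3 versus 4 or higher under the SAP 8.2.3 efficacy baseline, to the Firth model and the risk-difference estimate in SAP 10.1.2 and Protocol 11.3. One binary term suits about 25 expected events better than several categories.

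- **Missing score.** State a rule, for example classification from the pre-dose Day 1 record of CPAP/BiPAP or HFNC use. It should also cover subjects randomized but never dosed.
- **Sensitivity and tipping-point fits.** Keep the term, because these test the primary result. The number of tipping-point fits does not change.
- **Secondary endpoints.** Add it to the all-cause mortality and intubation models. Leave CPAP/BiPAP, HFNC, ECMO and length of stay as planned. This splits the common model in SAP 10.2.1, but those tests are descriptive.
- **Subgroups.** The term may be left out, and the SAP should say so. Keeping it in fits of 40–62 subjects would cost 0.9–1.5 points of power at OR 1 and 0.1–1.1 at OR 3.
- **Interim.** Align the IDMC SAP if its analysis uses the same model.

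The cost is wording in two or three documents, one more parameter, and about 0.3–0.5 points of power if severity is not prognostic (up to 0.5 at OR 1.5). The Schedule of Assessments grid and the CRF are not in the available text, so the sponsor should confirm when the pre-randomization NIAID score is taken.

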### 10.1.3 Sensitivity Analyses for Progression to Tracheal Intubation or Death Prior to Tracheal Intubation

The mITT Analysis Set will be used as sensitivity analysis for the primary analysis with the same endpoint and model as specified in Section 10.1.2.

The ITT Analysis Set will be used as sensitivity analysis for the primary analysis assuming that subjects with less than 28 days of the Treatment Period (i.e., who discontinued from the study prematurely) and without documented intubation or death progressed to tracheal intubation or died prior to tracheal intubation using the same model as specified in Section 10.1.2.

Another sensitivity analysis will be conducted where the subjects who started use of anti-COVID-19 drugs after randomization will be considered as having experienced progression to tracheal intubation or died prior to tracheal intubation using the same model as specified in Section 10.1.2.

For reference purpose, a complete-case analysis (i.e., including only subjects who completed Day 28 or who died) will also be done.

### 10.1.3.1 Tipping Point Analysis

Missing primary efficacy outcome is defined as subjects with less than 28 days of the Treatment Period and without documented tracheal intubation or death. Missing primary efficacy outcome will be imputed in a systematic way as having or not having experienced the event, where the event is progression to tracheal intubation or death prior to tracheal intubation.

The purpose of the tipping point analysis is to show which combination of imputed values for the missing primary efficacy outcome may alter the result of the primary efficacy comparison. Thus, the tipping point analysis will only be performed if the primary efficacy analysis indicates a significant treatment effect.

Analyses will be run for each possible combination of missing outcomes considering the subjects as not interchangeable: for each subject with missing outcome the two possible outcomes (1 = having experienced the event, 0 = not having experienced the event) will be imputed in combination with every other subject with missing outcome with the two possible outcomes of these subjects. This will result in  $2^m$  possible combinations, with  $m$  being the number of subjects with missing outcome in both treatment group combined. All combinations of imputed data will be analyzed with the primary model as specified in Section 10.1.2.

The possible combinations will be derived as illustrated below for up to 4 subjects:

[figure not shown]
Number of Subjects With Missing Outcome	Possible Combinations* (Number of Analyses)	Proportion of Subjects Experiencing the Event
1	2 (0, 1)	0, 1
2	4 (00, 01, 10, 11)	0, 0.5 (twice), 1
3	8 (000, 001, 010, 011, 100, 101, 110, 111)	0, 0.33 (three times), 0.67 (3 times), 1
4	16 (0000, 0001, 0010, 0011, 0100, 0101, 0110, 0111, 1000, 1001, 1010, 1011, 1100, 1101, 1110, 1111)	0, 0.25 (4 times), 0.5 (6 times), 0.75 (4 times), 1

0 = subject did not experience the event, 1 = subject experienced the event

The treatment comparisons obtained from each combination will be classified into favorable (1-sided p-value < 0.025 symbolized by black color) and unfavorable (1-sided p-value ≥ 0.025 symbolized by red color) and depicted in a graph where the x-axis and y-axis will present the proportion of subjects with missing endpoint imputed as having experienced the event for CSL312 + SOC and placebo + SOC, respectively.

If each subject with missing outcome is combined with every other subject with missing outcome, there will be more than one combination with the same proportion of subjects having experienced the event if  $m > 1$  as illustrated in the last column of the above table. The median p-value of the combinations with the same proportion of subjects having experienced the event will be used in the graph.

An example for such a graphical display could look like this (the axes represent the number of missing subjects in this graph, but maybe translated to the proportion of subjects having or not having experienced the event):

Red: 1-sided p-value ≥ 0.025, black: 1-sided p-value < 0.025

The number of subjects with missing outcome in this study is expected to be small. However, if the number of subjects with missing outcome is large and all possible  $2^m$  combinations become too cumbersome for above described method to be implemented, an alternative method will be used (e.g., if appropriate, treating subjects as interchangeable, i.e., no covariates besides treatment will be included in the logistic regression model and there will

be  $(a+1)*(b+1)$  combinations for possible outcomes where a and b are the number of subjects with missing outcome in each treatment group, respectively).

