## 7 General Considerations

Datasets submitted to regulatory agencies will be created according to Clinical Data Interchange Standards Consortium (CDISC) standards. Submission data will be provided in Study Data Tabulation Model (SDTM) format. Analysis data will be provided in Analysis Data Model (ADaM) format.

Statistical Analysis System (SAS) version 9.4 or higher will be used to perform all data analyses.

Continuous variables will be summarized in terms of the number of observations (n), mean, SD, median, first quartile, third quartile, minimum and maximum. Other descriptive statistics (e.g., standard error [SE], CV%) may be reported when appropriate. For repeated assessments of continuous variables, the change from baseline will also be summarized. Categorical variables will be summarized using frequency counts and percentages. Analyses that use other descriptive statistics will have the specific descriptive statistics identified with the analysis in the applicable SAP section.

Statistical tests will be 1-sided and will be performed at an alpha level of 0.025 unless otherwise stated.

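### The tipping-point graph colours each cell by its median p-value, so a cell near the 0.025 boundary can mix significant and non-significant allocations without showing it

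*SAP*

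**What the plan says.** SAP 10.1.3.1 states that the tipping-point analysis is meant to "show which combination of imputed values for the missing primary efficacy outcome may alter the result of the primary efficacy comparison". It is run only if the primary analysis is significant.

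The method has three steps:

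- **Enumeration.** "Analyses will be run for each possible combination of missing outcomes considering the subjects as not interchangeable". With m missing outcomes over both arms this gives 2^m data sets.
- **Model.** "All combinations of imputed data will be analyzed with the primary model as specified in Section 10.1.2". That model is the Firth logistic regression of SAP 10.1.2, with treatment, age, gender, country and comorbidity.
- **Display.** The comparison from each combination is to be "classified into favorable (1-sided p-value < 0.025 symbolized by black color") or unfavourable (red) otherwise, and plotted against the proportion of missing subjects imputed as events in each arm. Because several combinations share the same proportions, the section adds: "The median p-value of the combinations with the same proportion of subjects having experienced the event will be used in the graph".

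The text asks for no minimum, maximum, range or share of overturning combinations in a cell. SAP 10.4 names this section as the assessment of the impact of missing data on the primary result.

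**The concern.** Treating subjects as not interchangeable matters only because, in an adjusted model, the p-value depends on which subjects are imputed as events and not just on how many. The 2^m fits capture that variation, and the median then removes it from the picture. The section also pulls two ways: it classifies each combination, then plots one summary for many combinations.

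The practical stake is how the graph is read. It appears only after a significant result, and a reader will take a black cell to mean that the conclusion survives that pattern of missing outcomes. In a mixed cell this holds for some allocations and fails for others, and the graph does not say so.

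**Working it through.** **1. Allocations per cell.** Let a and b be the numbers missing in the CSL312 and placebo arms, and let cell (i, j) have i and j of them imputed as events. The cell holds k = C(a,i) × C(b,j) allocations. The SAP's own table for four missing subjects, pooled over arms, lists 1, 4, 6, 4, 1 combinations. These are C(4,0) to C(4,4) and sum to 2^4 = 16, so that table reproduces. Split by arm as 2+2, there are 9 cells with k = 1, 2 or 4. The four corners always have k = 1, so there the median is the actual p-value.

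**2. Bound.** If the median of k p-values is below 0.025, the number at or above 0.025 is at most k/2 for even k and (k − 1)/2 for odd k. Thus k = 2 allows 1, k = 3 allows 1, k = 4 allows 2, k = 6 allows 3, k = 9 allows 4 and k = 36 allows 18. For example, p = 0.010 and 0.030 have median 0.020: the cell is black and half of it overturns the result. The same argument applies in reverse to red cells. The bound needs no assumption about the data.

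**3. Setting for the size.** The SAP 4.4 inputs are 30% versus 10%, 1-sided alpha 0.025, 80% power and 1:1 allocation. The usual formula gives n per arm = [1.960 × √(2 × 0.2 × 0.8) + 0.842 × √(0.3 × 0.7 + 0.1 × 0.9)]² / 0.2² = (1.109 + 0.461)² / 0.04 ≈ 61.6, so 62 per arm and 124 in total, as stated (power 0.803).

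**4. Simulation.** Trials of 62 per arm were generated at these rates and kept if significant with missing outcomes counted as non-events, which is the primary rule. All 2^m Firth fits were then run. The following are assumptions, because the documents give no figures:

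- age with mean 58 and SD 14, log-odds 0.04 per year;
- sex (60% in one category) and comorbidity (65%), each with log-odds 0.5;
- country split evenly, with no effect;
- missing subjects drawn at random from non-events, half per arm.

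Results with 1-sided Wald p-values:

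| Missing | Significant trials | Black cells | Mixed black | Mixed red | Trials with a mixed black cell |
|---|---|---|---|---|---|
| 2+2 | 150 | 1285 | 7 (0.5%) | 4 | 7 (5%) |
| 3+3 | 100 | 1465 | 21 (1.4%) | 12 | 16 (16%) |
| 4+4 | 40 | 863 | 17 (2.0%) | 18 | 13 (33%) |

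The mixed black cells with the largest hidden share were:

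- 2+2: 1 of 2 allocations (p 0.0190 and 0.0269, median 0.0230);
- 3+3: 4 of 9 (p from 0.0202 to 0.0265, median 0.0249);
- 4+4: 3 of 6 (p from 0.0188 to 0.0295, median 0.0238).

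**5. Robustness of the size.** With no covariate effects (3+3), mixed black cells still arose in 14 of 100 trials. Penalised likelihood-ratio p-values gave 3 of 100 trials (2+2) and 6 of 60 (3+3). A separate run of the same kind (200, 100 and 40 significant trials) gave 0.9% to 3.2% of black cells mixed. Mixed black against mixed red counts there were 15 and 16, 30 and 23, and 26 and 28 for 4, 6 and 8 missing. The largest p in its affected cells had a median of about 0.027 and never exceeded 0.036.

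**6. Worst-case corner.** This cell has every missing CSL312 subject as an event and every missing placebo subject as a non-event. In the separate run it was black in 196 trials, and in none of them did any other allocation lose significance. A further run found the same in 142 trials.

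**The case against.** The strongest reply is that the median is a fair summary and nothing important is hidden. Much of this stands.

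- **Direction.** A reader might infer that the graph systematically overstates robustness. The calculations do not support that: red cells conceal significant allocations about as often as black cells conceal non-significant ones.
- **Overall robustness.** A reader might also infer that an all-black graph cannot be trusted. The worst-case corner is a single allocation shown exactly, and when it was black no reversal was found anywhere in the simulated grids.
- **Size.** The per-trial percentages count any one mixed cell among 9, 16 or 25. Per black cell the figure is small and the hidden p-values are marginal. SAP 10.1.3.1 also expects few missing outcomes.
- **Other analyses.** SAP 10.1.3 adds an all-missing-as-event analysis, a complete-case analysis and an mITT analysis. SAP 10.3 makes every test but one descriptive, and no decision rule uses the graph. The figure shells are in a separate document not available here.
- **Fallback.** It is tempting to extend the criticism to the option for many missing outcomes, under which "no covariates besides treatment will be included in the logistic regression model". The SAP offers this only as an example, where appropriate, and says openly that covariates are dropped. All allocations in a cell then have the same p-value, so the median problem disappears.

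What remains is that mixed cells occur at the boundary, which is what a tipping-point graph is drawn to locate, and the planned display cannot show them. The all-missing-as-event analysis is itself a corner of the grid and does not reveal mixed interior cells.

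**Conclusion.** The point holds as a limited reporting defect. The display rule does not deliver the section's stated purpose near the boundary: a black cell can contain up to half non-significant allocations, and a red cell can contain significant ones. The bound is exact and follows from the SAP text alone.

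The practical size is roughly 0.5% to 3% of black cells with 4 to 8 missing outcomes, and the concealed p-values sit close to 0.025. That range rests on assumed covariate effects, on the planned event rates and on assumed numbers missing; the SAP gives no expected number. Single-allocation cells are exact. The confirmatory test, its error rate and the primary estimate are untouched. This is a cheap improvement, not a threat to the trial's conclusion.

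**What to change.** In SAP 10.1.3.1, replace the sentence on the median with a rule of this kind: *for each pair of proportions, the graph will show the share of combinations with 1-sided p ≥ 0.025, using three states: all combinations significant, mixed, none significant.* A two-colour version carries the same information if a cell is black only when its maximum p is below 0.025 and the share is printed in the cell. Adjust the legend and the classification sentence to match.

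Under the two-colour version, the black cells that would turn red in the simulation are the mixed ones: 7 of 1285, 21 of 1465 and 17 of 863. Under the three-state version, mixed red cells would also be shown as mixed.

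The cost is a sentence or two and a revised figure shell. Every fit is already planned, and the only downside is that a few boundary cells look less favourable. The fallback for many missing outcomes needs no change.
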